13.2.5 Access to Records

The investigator will make the office and/or hospital records of subjects enrolled in this study available for inspection by Vertex or its representative at the time of each monitoring visit and for audits. The records will also be available for direct inspection, verification, and copying, as required by applicable laws and regulations, by officials of the regulatory health authorities (FDA and others). The investigator will comply with applicable privacy and security laws for use and disclosure of information related to the research set forth in this protocol.

13.2.6 Subject Privacy

To maintain subject confidentiality and to comply with applicable data protection and privacy laws and regulations, all data, study reports, and communications relating to the study will identify subjects by assigned subject numbers, and access to subject names linked to such numbers will be limited to the site and the study physician and will not be disclosed to Vertex. As required by applicable laws and regulations in the countries in which the study is being conducted, the investigator will allow Vertex and/or its representatives access to all pertinent medical records to allow for the verification of data gathered in the CRFs/SAE Forms and the review of the data collection process. The FDA and regulatory authorities in other jurisdictions, including the IRB/IEC, may also request access to all study records, including source documentation, for inspection.

For sites participating in the US, and in accordance with the Health Insurance Portability and Accountability Act (HIPAA) and associated regulations, an executed HIPAA authorization will be obtained by the site from each subject before research activities may begin. Each HIPAA authorization will comply with all HIPAA requirements including authorization allowing the site access to and use of the subject's personally identifiable health information, authorization for the site to disclose such information to Vertex, the FDA, and other parties requiring access under the protocol, and statements as to the purpose for which such information may be used and for how long.

13.2.7 Record Retention

The investigator will maintain all study records according to current ICH E6 GCP Guidelines and/or applicable local regulatory requirement(s), whichever is longest, as described in the Clinical Trial Agreement. If the investigator withdraws from the responsibility of keeping the study records, custody will be transferred to a person willing to accept the responsibility and Vertex will be notified.

13.2.8 Study Termination

At any time, Vertex may terminate this study in its entirety or may terminate this study at any particular site. In addition, for reasonable cause, either the investigators or their IRBs/IECs may terminate the study at their center.

Conditions that may lead to reasonable cause and warrant termination include, but are not limited to:

- Subject or investigator noncompliance
- Unsatisfactory subject enrollment
- Lack of adherence to protocol procedures
- Lack of evaluable and/or complete data
- Potentially unacceptable risk to study subjects
- Decision to modify drug development plan
- Decision by the FDA or other regulatory authority

Written notification that includes the reason for the clinical study termination is required.

13.2.9 End of Study

The end of study is defined as the last scheduled visit (or scheduled contact) of the last subject.

13.3 Data Quality Assurance

Vertex or its designated representative will conduct a study site visit to verify the qualifications of each investigator, inspect clinical study site facilities, and inform the investigator of responsibilities and procedures for ensuring adequate and correct study documentation per current ICH E6 GCP Guidelines.

The investigator is required to prepare and maintain adequate and accurate case histories designed to record all observations and other data pertinent to the study for each subject. Study data for each enrolled subject will be entered into a CRF by study site personnel using a secure, validated, web-based electronic data capture (EDC) application. The investigator will affirm the completeness and accuracy of the data by signing each casebook before data lock. If applicable, periodic investigator signatures may also be required.

Instances of missing, discrepant, or uninterpretable data will be queried with the investigator for resolution.

13.4 Monitoring

The study will be monitored by Vertex or its designee in accordance with written procedures. Monitoring and auditing procedures developed or approved by Vertex for these activities comply with GCP regulatory requirements and guidelines.

The monitoring strategy may include onsite, remote, and central monitoring activities, in accordance with local regulations. The study site monitor will ensure that the study is conducted according to the protocol design and regulatory requirements.

13.5 Data Capture

Vertex will provide the study sites with secure access to and training on the EDC application sufficient to permit study site personnel to enter or correct information in the CRFs on the subjects for which they are responsible.

A CRF will be completed for each enrolled study subject. It is the investigator's responsibility to ensure the accuracy, completeness, clarity, and timeliness of the data reported in the subject's CRF. Source documentation supporting the CRF data will indicate the subject's participation in the study and will document the dates and details of study procedures, AEs, other observations, and subject status.

The investigator, or designated representative, will complete the CRF as soon as possible after information is collected.

The audit trail entry will show the user's identification information and the date and time of any correction. The investigator will provide formal approval of all the information in the CRFs, including any changes made to them, to endorse the final submitted data for the subjects for whom the investigator is responsible.

Vertex will retain the CRF data and corresponding audit trails. A copy of the final archival CRF will be placed in the investigator's study file.

13.7 Publications and Clinical Study Report

13.7.1 Publication of Study Results

Vertex is committed to reporting the design and results of all clinical studies in a complete, accurate, balanced, transparent, and timely manner, consistent with Good Publication Practices (GPP3).³²

Publication Planning: Vertex staff along with the lead principal investigators, the steering committee, and/or the publication committee will work together to develop a publication plan.

Authorship: Authorship of publications will be determined based on the Recommendations for Conduct, Reporting, Editing, and Publication of Scholarly Work in Medical Journals, which states that authorship should be based on the following 4 criteria:

- 1. Substantial contributions to conception and design, acquisition of data, or analysis and interpretation of data;
- 2. Drafting of the article or revising it critically for important intellectual content;
- 3. Final approval of the version to be published; and
- 4. Agreement to be accountable for all aspects of the work in ensuring that questions related to the accuracy or integrity of any part of the work are appropriately investigated and resolved.

All authors must meet conditions 1, 2, 3, and 4. All persons designated as authors should qualify for authorship, and all those who qualify should be listed. Contributions such as medical writing, enrollment of subjects, acquisition of funding, collection of data, or general supervision of the research group, alone, do not justify authorship.

Contributors: Contributors who meet fewer than all 4 of International Committee of Medical Journal Editors (ICMJE) criteria for authorship will not be listed as authors, but their contribution will be acknowledged and specified either as a group (e.g., "study investigators") or individually (e.g., "served as scientific advisor").

Publication Review: As required by a separate clinical study agreement, Vertex must have the opportunity to review all publications, including any manuscripts, abstracts, oral/slide presentations, and book chapters regarding this study before submission to congresses or journals for consideration.

13.7.2 Clinical Study Report

A clinical study report (CSR), written in accordance with the current ICH E3 Guideline, will be submitted in accordance with local regulations.

15 APPENDIX A: GUIDANCE ON SURGICAL PROCEDURES AND NON-SURGICAL ACUTE PAIN CONDITIONS

Representative eligible surgical procedures and non-surgical acute pain conditions are defined in Inclusion Criterion 5 (Section 8.1). Table 15-1 presents surgical procedures and non-surgical conditions representative of those which are NOT eligible.

Table 15-1Representative Ineligible Surgical Procedures and Non-surgical Conditions
Resulting in Acute Pain

Non-surgical Conditions
Pain resulting from presumed hollow organ obstructive pathology (e.g., pancreatitis, renal colic)
Pain presumed to be primarily visceral in origin (e.g., appendicitis, ovarian cysts, diverticulitis)
Pain in a subject with active cancer and/or undergoing treatment for same
TSA: total shoulder arthroplasty

3 MODIFICATIONS

3.1 Modifications to the Approved Clinical Study Protocol

Not applicable

3.2 Modifications to the Approved Statistical Analysis Plan

Not applicable

4 INTRODUCTION

This statistical analysis plan (SAP) for the final analysis is based on the most recent approved clinical study protocol (CSP), the most recent approved electronic case report form (eCRF), and the most recent approved eCRF completion guidelines. This SAP documents the planned statistical analysis of safety and effectiveness endpoints defined in the study protocol of VX22-548-107 and provides additional details and clarifications.

The Vertex Biometrics Department will perform the final statistical analysis of the efficacy and safety data; SAS® Version 9.4 Software (SAS Institute, Cary, North Carolina, USA) or higher will be used to generate all statistical outputs (tables, figures, listings and datasets).

The SAP (Methods) will be finalized and approved before the clinical data lock for the final analysis. Any revisions to the approved SAP will be documented and approved in an amendment to the SAP prior to the clinical database lock. Any revisions made to the SAP after the clinical data lock will be documented in the clinical study report for this study.

5 STUDY OBJECTIVES

5.1 Primary Objective

To evaluate the safety and tolerability of VX-548

5.2 Secondary Objective

To evaluate the effectiveness of VX-548 in treating acute pain

6 STUDY ENDPOINTS

6.1 Primary Endpoint

Safety and tolerability based on treatment-emergent adverse events (TEAEs), laboratory test results, vital signs, and ECGs

6.2 Secondary Endpoint

Subject perception of VX-548 effectiveness in treating pain at the end of treatment as measured by the proportion of subjects reporting good, very good, or excellent on a patient global assessment (PGA)

7 OVERALL DESIGN

This is a Phase 3, single-arm study evaluating the safety and effectiveness of VX-548 in treating acute pain (Figure 7-1 [surgical subjects] and Figure 7-2 [non-surgical subjects]).

Surgical Subjects

On Day 1, subjects will undergo a scheduled ambulatory surgical procedure with pain that is expected to last for at least 72 hours and that is expected to require no more than a short-term (i.e., <24-hour) admission. After surgery completion, a subject will be assigned to treatment if (1) the subject requests the first dose of study drug for pain relief, (2) the subject's pain is moderate or severe on the VRS (verbal categorical rating scale), and (3) the subject's pain is

 \geq 4 on the NPRS (numeric pain rating scale). If a subject does not meet the VRS and NPRS criteria within the protocol-specified time period for the surgical procedure they underwent (e.g., 4 hours for most procedures), the subject will not be eligible for this study.

Non-surgical Subjects

On Day 1, after completion of screening assessments and confirmation of eligibility, a subject will begin treatment if (1) the subject's pain is moderate or severe on the VRS, and (2) the subject's pain is \geq 4 on the NPRS. For a subject to be eligible, their pain must have been ongoing for \leq 48 hours at presentation.

All Subjects

Approximately 250 subjects will receive VX-548 (100 mg first dose, then 50 mg every 12 hours [q12h]). Subjects will continue to receive VX-548 for 14 days or until their pain resolves, whichever occurs first. An acetaminophen/ibuprofen combination may be used as a rescue medication for pain relief as needed (prn), starting any time after the first dose of study drug through Day 14, completion of study drug treatment due to pain resolution, or study drug discontinuation, whichever occurs first. Subjects will be permitted to take acetaminophen 650 mg/ibuprofen 400 mg every 6 hours (q6h) prn, up to a maximum of 2600 mg/1600 mg in any 24-hour period.

The following approach will be used to define pain resolution and completion of study drug treatment:

- 1. Pain is considered to be resolved and the study drug treatment will be considered completed if
 - a. a subject takes no study drug during a 48-hour period (i.e., skipped at least 4 consecutive doses due to pain resolution); and
 - b. a subject takes no more than 1 dose of acetaminophen/ibuprofen during each 24-hour period within the 48-hour period (i.e., no more than 2 doses in 48 hours).
- 2. If a subject stops taking study drug per Criterion 1a but does not meet Criterion 1b, they will be instructed to restart study drug (and prn rescue medication).
- 3. If a subject stops and restarts study drug (Criterion 2 above) and subsequently believes their pain is resolving and stops study drug a second time, they will be instructed to not restart study drug, regardless of whether the above criteria are met.
- 4. If a subject stops study drug a second time after the restart of dosing (Criterion 3 above) and then fulfills both Criterion 1a and 1b, the pain is considered resolved and study drug treatment will be considered completed. If the subject fulfills only Criterion 1a but not Criterion 1b after the restart of dosing, the pain is considered not resolved and study drug will be considered discontinued.

Note: If subject stops study drug due to pain resolution less than 48 hours before the last scheduled dose of study drug (i.e., stops after the second dose on Day 12) and therefore cannot meet Criterion 1a by Day 14, the subject will be considered to have completed study drug dosing as long as they also meet Criterion 1b.

Figure 7-1 VX22-548-107 Study Design (Surgical Subjects)

NPRS: numeric pain rating scale; VRS: verbal categorical rating scale

Notes: After surgery completion, a subject will be assigned to treatment if (1) the subject requests the first dose of study drug for pain relief, (2) the subject's pain is moderate or severe on the VRS, and (3) the subject's pain is \geq 4 on the NPRS. If a subject does not meet the VRS and NPRS criteria within the protocol-specified, procedure-specific time period, the subject will not be eligible for this study. Figure is not drawn to scale.

Figure 7-2 VX22-548-107 Study Design (Non-surgical Subjects)

NPRS: numeric pain rating scale; VRS: verbal categorical rating scale

Notes: After completion of screening assessments and confirmation of eligibility, a subject will be assigned to treatment if (1) the subject's pain is moderate or severe on the VRS, and (2) the subject's pain is \geq 4 on the NPRS. Figure is not drawn to scale.

7.1 Sample Size and Power

Approximately 250 subjects are planned to be enrolled. With 250 subjects, there is a 92% probability of observing an AE in at least 1 subject if the true incidence is 1% and a 99% probability of observing an AE in at least 1 subject if the true incidence is 2%.

7.2 Randomization

This is a single-arm study with no randomization.

7.3 Blinding and Unblinding

This is an open-label study.

8 ANALYSIS SETS

8.1 All Subjects Set

The **All Subjects Set** is defined as all subjects who were enrolled (defined as subject having data in the clinical database). The All Subjects Set will be used for individual subject data listings and disposition summary tables.

8.2 Safety Set

The **Safety Set** is defined as all subjects who have received at least 1 dose of study drug. The Safety Set will be used for all safety analyses.

8.3 Full Analysis Set

The **Full Analysis Set (FAS)** is defined as all subjects who have received at least 1 dose of study drug. The FAS will be used for effectiveness analyses.

9 STATISTICAL ANALYSIS

9.1 General Considerations

The Schedule of Assessments is provided in Section 3 of the CSP. The precision standards for reporting variables are provided in an internal Biometrics document that specifies the programming rules including the precision for derived variables.

All individual subject data for subjects who have received at least 1 dose of study drug will be presented in individual subject data listings.

Continuous variables will be summarized using the following descriptive summary statistics: the number of subjects (n), mean, standard deviation (SD), median, minimum value (min), and maximum value (max).

Categorical variables will be summarized using counts and percentages.

Baseline value, unless specified otherwise, will be defined as the most recent non-missing measurement (scheduled or unscheduled) collected before the first dose of study drug.

For ECGs, the baseline value will be defined as the average of the most recent non-missing measurements (scheduled or unscheduled) collected before the first dose of study drug, expected to be the triplicate predose measurements on Day 1.

Change (absolute change) from baseline will be calculated as post-baseline value – baseline value.

Treatment-emergent (TE) Period will include the time from the first dose of study drug to the Safety Follow-up Visit or to the completion of study participation (as defined in Section 9.1.7 of the CSP), whichever occurs first.

Unscheduled visits: Unscheduled visit measurements will be included in the analysis as follows:

• In scheduled visit windows per specified visit windowing rules

- In the derivation of baseline
- In the derivation of maximum and minimum values during the TE period, and maximum and minimum change from baseline values during the TE period for safety analyses
- In individual subject data listings as appropriate

Visit windowing rules: The analysis visit windows for protocol-defined PGA entries, which are provided by the subject in a dosing diary, are provided in Appendix A. All safety assessments are analyzed according to their nominal visits.

Outliers: No formal statistical analyses will be performed to detect and/or remedy the presence of statistical outliers.

Multiplicity: Only descriptive analyses will be performed; no statistical hypothesis testing will be performed.

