PGA		X			X	X	X		Recorded in the e-diary ^d ; Section 11.4.1. Subjects should still complete the PGA even if the specified dose is not taken. Day 2: To be completed after the third study drug dose (approximately 24 hours after the first dose). Day 7: Completed after the first study drug dose on Study Day 7 (whether or not this coincides with the date of the Day 7 Visit). Day 14 or EDV: Completed after final study drug dose for subjects still taking study drug on Day 14. Subjects who have discontinued or completed study drug treatment should complete the PGA at home within approximately 24 hours after the last (or presumed last) dose of study drug rather than waiting for their scheduled visit.
Vital signs			X (postdose) ^b		Х	х	Х	Х	Vital signs will be collected after a \geq 5-minute rest (seated or supine) and before any 12-lead ECG assessment or blood sampling; Section 11.5.3.
Standard 12-lead ECG	at discharg	ours after first e or before lea ility, as applic	ving medical		X (4 hours after a dose) ^e	X (4 hours after a dose) ^{e,f}	X	(X)	Required at SFU only if any clinically significant abnormalities were noted on a prior ECG. Standard 12-lead ECGs will be performed in triplicate after a ≥5-minute rest (supine); these will be done after taking vital signs and before any procedures that may affect heart rate (e.g., blood sampling); Section 11.5.4.

Table 3-4Study VX22-548-107: Treatment Period and Safety Follow-up Visit (All Subjects)

Table 3-4Study VX22-548-107: Treatment Period and Safety Follow-up Visit (All Subjects)

Event/Assessment ^a	Day 1	Day 2	Discharge ^b	Day 4 (± 1 day)	Day 7 (± 1 day)	Day 14 (+ 3 days)	End of Dosing Visit ^c	Safety Follow-up Visit Day 28 (± 2 days)	Comments
Symptom-directed PE				As applicable					Symptom-directed PEs will occur at any time during the study if triggered by AEs or if deemed necessary by the investigator; Section 11.5.3.
Focused PE (surgical subjects only)								Х	Assessment of wound healing at the operative site; Section 11.5.3.
Complete PE								(X)	Required at SFU only if a clinical finding during the Treatment Period requires follow up, in which case the subject must have a clinic visit; Section 11.5.3.
C-SSRS			X (postdose) ^b		Х	Х	X		Section 11.5.5
Urine β-hCG						Х	Х	Х	All female subjects of childbearing potential; Section 11.5.2.
Serum chemistry			X (postdose) ^b			Х	X	(X)	Required at SFU only if a clinical finding during the Treatment

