- ^c If a subject discontinues or completes study drug treatment for any reason before Day 14, including AEs (considered treatment discontinuation) or reaching pain resolution (considered treatment completion), an EDV should be scheduled to occur as soon as possible after treatment discontinuation or after pain resolution criteria are met (as applicable), and the Day 14 Visit will not be required. If the EDV occurs within or prior to the Day 7 visit window, the Day 7 Visit will also not be required. Subjects who discontinue or complete study drug treatment before Day 14 will be required to complete the Safety Follow-up Visit. In the unlikely event that the EDV is delayed and occurs 28 days or later following the first dose of study drug, then a separate Safety Follow up Visit will not be required.
- ^d For all e-diary assessments, a paper version will be available as a back-up option.
- ^e Refer to Section 9.6 for instructions on dose and visit scheduling on days of postdose ECGs.
- f Subjects who have their Day 14 Visit after Study Day 14 (per the visit window) and thus are no longer taking study drug will have an ECG any time that day rather than 4 hours postdose.
- ^g For subjects who remain on study drug treatment at Day 14, only 1 dose of study drug should be taken on that day, and it will be the last dose of study drug for these subjects.

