11.5.4 Electrocardiograms

Standard 12-lead ECGs will be performed in triplicate using a machine with printout. Additional standard 12-lead ECGs will be performed at any other time if clinically indicated. The performance of all ECGs will adhere to the following guidelines:

- The ECG will be done before blood draws or any other procedures that may affect heart rate.
- The subject will be instructed to rest (supine) for at least 5 minutes before having an ECG.
- The test should be performed in the supine position.

The acceptable window for the 4-hour postdose ECG is \pm 30 minutes relative to the scheduled nominal time.

A printout of the ECG traces will be made for safety review by the investigator and maintained with source documentation. All traces will be centrally evaluated by a qualified cardiologist. Clinically significant ECG abnormalities occurring during the study through the Safety Follow-up Visit will be recorded as AEs.

To ensure safety of the subjects, a qualified individual at the study site will make comparisons to baseline measurements. If the median QTcF is increased by >60 msec from the baseline or the median absolute QTcF value is \geq 500 msec for any scheduled or unscheduled ECGs (performed in triplicate), 2 additional ECGs (performed in triplicate) will be performed approximately 2 to 4 minutes apart to confirm the original measurement. If the median QTcF value from either of these repeated ECGs remains above the threshold value (>60 msec from baseline or \geq 500 msec), the subject should discontinue dosing. For safety monitoring after discontinuation, a single ECG will be repeated at least hourly until QTcF values from 2 successive ECGs fall below the threshold value that triggered the repeat measurement.

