9.4.3 Electrocardiogram

For the treatment-emergent ECG measurements, a summary of observed values and change from baseline values will be provided at each visit and time point, as applicable, for the following ECG measurements: heart rate (HR; beats per minute [bpm]), PR interval (msec), RR interval (msec), QRS duration (msec), QT interval (msec), and QT corrected for HR intervals (QTcF [msec]).

The number and percentage of subjects meeting threshold analysis criteria during the TE period will be summarized. The threshold analysis criteria are provided in Appendix D. A listing containing individual subject measurements meeting the threshold value criteria at any time point will be provided. This listing will include data from both scheduled and unscheduled visits.

In addition, the number and percentage of subjects by maximum treatment-emergent value of QT/QTcF intervals, categorized as \leq 450 msec, >450 msec and \leq 480 msec, >480 msec and

 \leq 500 msec, and >500 msec, as well as maximum treatment-emergent change from baseline value of QT/QTcF intervals, categorized as \leq 0 msec, >0 and \leq 30 msec, >30 and \leq 60 msec, and >60 msec, will be provided.

ECGs are performed in triplicate. The mean of the ECG measurements will be used as the ECG value for summaries of observed values and change from baseline values. All reported ECG measurements will be used to conduct threshold analyses and to assess maximum treatment-emergent values.

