12 LIST OF APPENDICES

Appendix A: Analysis Visit Windows for Effectiveness Assessments

Table 12-1 Analysis Visit Windows for Effectiveness Assessments			
Assessment	Visit/Timepoint	Target Study Day	Analysis Visit Window (in study days/timepoints)
PGA	EDV	After treatment completion/disconti nuation	First assessment between 0 and 48 hours after subject's last dose of VX-548

Note: If no PGA measurement is available within the EDV visit window, PGA at EDV will be imputed with the previous PGA measurement, if available.

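### The nominal Day 14 ECG row can mix 4-hour postdose tracings with tracings taken on Study Days 15-17 after dosing has ended; SAP 9.4.3 should add two sub-rows

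*SAP*

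**What the plan says.** **Timing of the Day 14 ECG.** Protocol Table 3-4 schedules it "4 hours after a dose". Protocol 11.5.4 sets the tolerance: "The acceptable window for the 4-hour postdose ECG is" 30 minutes either side of the nominal time. Protocol 9.6 asks that dosing on Study Day 14 be arranged around this ECG, and lets a dose be held back for up to 3 hours to achieve it.

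**Late visits.** The Day 14 Visit has a +3-day window in Table 3-4. Footnote f covers subjects seen after Study Day 14, who are "no longer taking study drug will have an ECG any time that day rather than 4 hours postdose". Footnote g makes the single Study Day 14 dose the last one.

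**Analysis.** SAP 9.1 states: "All safety assessments are analyzed according to their nominal visits". For ECGs, SAP 9.4.3 provides that "a summary of observed values and change from baseline values will be provided at each visit and time point, as applicable". On triplicates it says: "The mean of the ECG measurements will be used as the ECG value for summaries of observed values and change from baseline values". The SAP's only analysis window tied to the last dose is in Appendix A and is for the PGA ("First assessment between 0 and 48 hours after" the last dose). ECGs have none.

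**The concern.** The protocol plans two kinds of ECG under one visit name: one at a fixed time after a dose, and one with no fixed relation to a dose. The late tracings are not deviations. The SAP's stated rule assigns data by visit name, and it defines no Day 14 time point for a tracing taken after the last dose. A programmer who follows SAP 9.1 literally would put both kinds in one row.

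ECGs are part of the primary endpoint. Day 14 is the only scheduled 4-hour postdose ECG at the end of the full 14-day course, and the protocol goes to some trouble to obtain that timing. A mean change that combines both kinds of tracing cannot be read as a 4-hour postdose result, and the table would not show how far it departs from one.

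**Working it through.** The plan gives no figure for this row. Its only computed probabilities (SAP 7.1, chance of seeing at least one AE in 250 subjects) reproduce and do not bear on the point: 1 - 0.99^250 = 0.919 (stated 92%) and 1 - 0.98^250 = 0.994 (stated 99%).

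**Step 1: on-schedule tracing.** 4 h ± 0.5 h gives 3.5 to 4.5 h after the Study Day 14 dose.

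**Step 2: late tracing.** Let d be the Study Day of the visit (15, 16 or 17), E the ECG clock time and L the clock time of the last dose on Study Day 14, both in hours. Then

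hours since last dose = 24 × (d - 14) + E - L.

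The documents fix d but not E or L, so three sets of clock times are shown:

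- A: no restriction on either clock time.
- B (assumed): dose between 00:00 and 15:00 (a morning slot, held back up to 3 h); ECG between 08:00 and 17:00.
- C (assumed): dose at 20:00 or at 08:00; ECG between 08:00 and 17:00.

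| Study Day | A | B | C, dose 20:00 | C, dose 08:00 |
|---|---|---|---|---|
| 15 | above 0 to under 48 h | 17-41 h | 12-21 h | 24-33 h |
| 16 | 24-72 h | 41-65 h | 36-45 h | 48-57 h |
| 17 | 48-96 h | 65-89 h | 60-69 h | 72-81 h |

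For example, B on Day 15 runs from 24 + 8 - 15 = 17 to 24 + 17 - 0 = 41. Under B and C together the range is 12 to 89 h, with no overlap with 3.5-4.5 h. Overlap needs extreme clock times: a dose at 22:00 and an ECG at 02:00 gives 24 + 2 - 22 = 4 h.

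**Step 3: where each tracing goes.** Study Days 15-17 lie inside the treatment-emergent period (first dose to Safety Follow-up, SAP 9.1), so late tracings are not removed. Each triplicate is averaged, labelled with its nominal visit and summarised. Nothing in the SAP gives a late Day 14 Visit tracing a different row.

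**Step 4: what pooling does to the mean.** Suppose a share f of the row is late, the mean 4-hour change is D, and a fraction r of D remains in late tracings. The row then shows D × [(1 - f) + f × r]. None of f, D or r is in the documents. Purely as an illustration, with D = 10 msec:

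| f | r = 0 | r = 0.5 |
|---|---|---|
| 0.10 | 9.0 | 9.5 |
| 0.25 | 7.5 | 8.75 |
| 0.50 | 5.0 | 7.5 |
| 0.75 | 2.5 | 6.25 |

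This shows the mechanism and is not an estimate for this trial.

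**The case against.** The strongest reply is that the SAP already accommodates the split. SAP 9.4.3 speaks of time points as well as visits, 4 hours postdose is a protocol time point, and footnote f itself sets the late ECG apart from it. SAP 9.1 also refers to an internal programming document that is not public. This stands in part: pooling is possible, not certain. A reader might infer that the SAP mandates pooling, and the text does not go that far. But permission is not a rule. No post-dosing Day 14 time point is defined, and the one positive instruction is to use the nominal visit.

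The second reply is that the row carries little weight. The study is single-arm and descriptive, with no hypothesis tests and no pharmacokinetics. In surgical subjects the predose ECG follows anaesthesia and perioperative drugs. QT safety is also covered by the threshold counts and maximum-value categories: "All reported ECG measurements will be used to conduct threshold analyses and to assess maximum treatment-emergent values". All of this stands, and it limits the point to a small improvement.

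Third, the End of Dosing Visit row also mixes times since dose. That is true, but Table 3-4 sets no postdose time for that ECG, and it is a separate nominal visit.

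Two further inferences should be resisted. Late tracings need not be free of drug effect: footnote f says only that dosing has ended, the documents give no half-life, and an early Day 15 tracing could be a few hours postdose. Nor is the Day 7 row shown to be a clean 4-hour comparison, because a subject may be within a 48-hour pause in dosing (protocol 9.1) at that visit.

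**Conclusion.** The point holds as a cheap improvement to one descriptive summary. As written, the plan allows the Day 14 observed-value and change-from-baseline row to combine 3.5-4.5 h tracings with tracings generally taken from about half a day to several days after the last dose. The hour ranges assume a last dose on Study Day 14 and the clock times stated above.

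The share of late visits is not given, so the effect on the mean is unknown. A reader might infer that a QTcF signal would be hidden or materially understated. The documents do not support that: they give no expected effect, no late-visit rate and no residual-exposure data. Threshold and maximum-value analyses are unchanged, and no error rate or power is involved.

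**What to change.** In SAP 9.4.3, keep the overall nominal Day 14 row so that no data are lost. Beneath it, add two sub-rows for observed value and change from baseline, using triplicate means:

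- *Study Day 14, 4 h postdose (3.5-4.5 h)*
- *Day 14 Visit after Study Day 14 (after last dose)*

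Give n and the minimum and maximum hours since last dose for each sub-row. Study Day 14 tracings outside 3.5-4.5 h stay in the overall row and are listed. Leave the threshold and maximum-value analyses as they are. The label of the second sub-row should say only that the last dose has been taken; the hours since last dose then show how recent it was.

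**Cost.** One programming rule and two row labels, made by SAP amendment before database lock as SAP section 4 provides. No protocol change is needed. Dose times are already recorded (protocol 9.6). ECG clock times are assumed to be recorded, since a 30-minute tolerance cannot be checked without them, but the documents do not state it. The drawback is a smaller n in each sub-row.
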